## LIST OF ABBREVIATIONS

AE	Adverse Event/Adverse Experience
BCTQ	Boston Carpal Tunnel Syndrome Questionnaire
CBC	Complete Blood Count
CFR	Code of Federal Regulations
CRF	Case Report Form
CTS	Carpal Tunnel Syndrome
DSMB	Data and Safety Monitoring Board
DSMP	Data and Safety Monitoring Plan
FDA	Food and Drug Administration
GCP	Good Clinical Practice
HIPAA	Health Insurance Portability and Accountability Act
HUVECs	Human Umbilical Vein Endothelial Cells
IB	Investigator's Brochure
ICL	Immunochemical Core Laboratory
IND	Investigational New Drug Application
IRB	Institutional Review Board
PHI	Protected Health Information
PI	Principal Investigator
SAE	Serious Adverse Event/Serious Adverse Experience
SABG	Senescence-Associated $\beta$ -Galactosidase
SASP	Senescence-Associated Secretory Phenotype
SOP	Standard Operating Procedure
SSCT	Subsynovial Connective Tissue
SSS	Symptom Severity Score
UPIRTSO	Unanticipated Problem Involving Risk to Subjects or Others
WCBP	Women of Child Bearing Potential

## Study Summary

Title	Phase 2 Clinical Trial of Fisetin to Treat Carpal Tunnel Syndrome (FITCATS)
Running Title	FITCATS
Protocol Number	21-010406
Phase	Phase II
Methodology	Interventional
Overall Study Duration	2 years
Subject Participation Duration	180 days
Single or Multi-Site	Single Site Study
Objectives	To evaluate the effectiveness of treatment of Fisetin to treat mild-moderate Carpal Tunnel Syndrome (CTS)
Number of Subjects	100 screened, 40 enrolled
Diagnosis and Main Inclusion Criteria	Adult men and women between age 21 and 80 who have a clinical diagnosis of Carpal Tunnel Syndrome (CTS)
Study Product, Dose, Route, Regimen	This study will involve a regimen with Fisetin, 100 mg capsules/ (~20 mg/kg body weight/day)
Duration of Administration	2 consecutive days and, after 1 month, another 2 consecutive days
Statistical Methodology	This is a phase 2 trial to determine if Fisetin has any effect on CTS, powered based on the results of known effective treatments of CTS. The primary hypothesis is that the Boston CTS questionnaire score will improve by 1 point from pre-treatment to 60 days post-treatment. The secondary hypothesis is that clinical improvement will be proportional to the effect in reducing blood markers of cellular senescence

## 1 Introduction

This document is a protocol for a human research study. This study will be carried out in accordance with the applicable United States government regulations and Mayo Clinic research policies and procedures.

### 1.1 Background

Carpal tunnel syndrome (CTS), a compression neuropathy of the median nerve at the wrist, causes numbness and weakness in the hand, resulting in loss of hand dexterity, sensation, and strength. CTS is the most commonly diagnosed disorder of the upper extremity, with a lifetime risk of 25% to 30%. It is more common in women than in men, and typically develops in people aged 45 and older. The etiology of CTS is unknown in most cases, but it is associated with other disorders of aging as well as disorders known to be associated with cellular senescence, such as diabetes and obesity. One of the most characteristic findings in CTS is progressive non-inflammatory fibrosis of the subsynovial connective tissue (SSCT) within the carpal tunnel. Current treatment of CTS is empiric, with activity modification and steroid injections for mild to moderate cases, and surgical decompression for more severe disease. Currently, roughly 50% of all patients with CTS require surgery. A better, mechanistically based, non-surgical treatment for CTS is urgently needed.

We have identified an increased burden of senescent cells in the SSCT as a potential mediator of CTS, as evidenced by increased expression of p16INK4A, CTGF/CCN, and TGF- $\beta$  and dysregulation of multiple transcriptional markers of senescence. Further, we have preliminary data showing that senolytics, including Fisetin, can clear senescent SSCT cells *in vitro*. Fisetin has already been approved by the FDA to be used in clinical trials and is currently being used at Mayo in several Phase 2 trials to treat: senescence associated fragility in older women (AFFIRM, ClinicalTrials.gov Identifier: NCT03675724); CoV infection (NCT04476953); diabetic and chronic kidney disease (NCT03325322), and to alleviate age-related osteoporosis (NCT04313634).

Like the AFFIRM trial, our proposed FITCATS trial will enroll approximately 40 subjects with mild-moderate CTS and evidence of senescence from blood markers into a short term (180 days) prospective phase 2 study of Fisetin therapy, using as outcome measures a well-accepted patient reported outcome questionnaire (Boston CTS questionnaire, BCTQ) as well as reduction from baseline in senescence markers in the blood, including SASP factors and inflammatory markers. Based on the known performance of the BCTQ, we estimate that a sample size of 40 will be sufficient to show a clinically important difference in outcome, if it is present. A placebo control is inappropriate, because other, effective (but more invasive-so blinding is also not possible) treatments are available, and our own experience in a previous CTS trial (DUCATS; NCT02219555) has shown that patients will not agree to enroll in a trial with randomization to a placebo arm, even for periods as short as one month. Mayo sees over 1,000 patients with CTS each year, so completing this study with 40 subjects within a 2-year time frame is feasible. Each subject will be enrolled for a six-month period. Subjects may withdraw at any time, for any reason.

If this short-term Phase 2 study shows that Fisetin reduces symptoms and senescence markers and increases function in subjects with mild-moderate CTS, we will then proceed to a larger Phase 3 study comparing Fisetin to a known effective non-surgical treatment, steroid injection.

## **1.2 Investigational Agent**

See Investigator's Brochure

## **1.3 Preclinical Data**

See Investigator's Brochure

## **1.4 Clinical Data to Date**

The senolytic drug used in this study is Fisetin. This proposal outlines use of the dietary supplement Fisetin dosed twice for a 2-day period one month apart.

To our knowledge, there are no published studies utilizing Fisetin for CTS. Several studies involve use of Fisetin for its anti-oxidative and anti-apoptotic effects in animal models. Fisetin may reduce oxidative stress, alleviate hyperglycemia, and improve kidney function. Based on our preclinical experience with 46 agents/drugs examined and recent studies in Fisetin, these senolytics induce apoptosis of senescent cells *in vitro* with minimal effects on non-senescent or healthy cells. Removal of these senescent cells has broad potential implications including improvements in CTS symptoms and more general metabolic parameters. Preliminary data have shown that markers of cellular senescence are elevated in the carpal tunnel synovium of patients with CTS. We hypothesize that Fisetin will reduce these markers, and thereby improve the symptoms of CTS in these patients.

## **1.5 Dose Rationale**

See Investigator's Brochure

## **1.6 Risks and Benefits**

In this study, we will examine the effect of Fisetin as a senolytic agent in humans, which may have immense potential as a treatment for CTS in addition to other clinical benefits. As an off-target effect, removal of senescent cells may allow for functional improvement of neighboring or distant cells and tissues, allowing enhancement in overall function.

Based upon the review of the published literature and our pre-clinical data, we do not anticipate the occurrence of serious adverse events with the prescribed regimen in this study. We have identified a variety of drug-drug interactions and behavior activities (caffeine, tobacco/nicotine consumption) for which we established exclusion criteria or modification plans to minimize associated risks. We have also followed the Clinical Trials Facilitation and Coordination Group's protocol recommendations for including women of childbearing potential. Therefore, the risks of using this drug are likely minimal compared to the anticipated benefits and the knowledge that may be gained from these clinical investigations.

## 2 Study Objectives

[figure not shown]
### Primary Objective

To test the efficacy of the senolytic drug (Fisetin) in reducing the symptoms of CTS, as measured by the Boston CTS questionnaire, a validated measure of CTS outcome, in 20 men and 20 women with Carpal Tunnel Syndrome (CTS).

### Secondary Objective

To study the effect of Fisetin on circulating and urine biomarkers of senescence in subjects with CTS, and to identify any composite clinical and biomarker measures that may improve the ability to predict outcome after treatment for CTS.

## 3 Study Design

### 3.1 General Description

This study is a phase II study evaluating the efficacy of the senolytic drug Fisetin in reducing symptoms (primary outcome) and senescent cell abundance by markers of senescence and inflammation (secondary outcomes) in men and women with CTS.

Subjects will be screened and interested qualified subjects will be consented and offered participation in this trial.

Once consent has been obtained, subjects will be screened, baseline values will be obtained, and subjects will begin treatment and follow-up for the next 180 days. The overall study duration is 2 years.

### 3.2 Number of Subjects

A total of 20 adult men and 20 adult women between age of 21 and 80 who have a clinical diagnosis of Carpal Tunnel Syndrome.

### **3.3 Duration of Participation**

Participants in this study will remain in this study for the duration of 180 days (6 months), but we will request that they allow us to retain their blood and urine specimens indefinitely for possible future analysis, depending on the outcome of the study.

### **3.4 Primary Study Endpoints**

In this pilot study, our primary endpoint will be a decrease in CTS symptoms at 60 days (2 months) compared to baseline, as measured by the Boston CTS questionnaire.

### **3.5 Secondary Study Endpoints**

Our secondary endpoints will be the change in circulating and urine biomarkers of senescence from enrollment to the 60-day end point, and the long-term symptom outcome at 180 days.

### **3.6 Primary Safety Endpoints**

Safety endpoints are undertaken with the measurement of safety laboratory testing, adverse event monitoring, and subject questionnaires.

### **3.7 Identification of Source Data**

The following source data will be directly recorded on the Case Report Form (CRF) or electronic Case Report Form (eCRF) in REDCap

- Subject Eligibility Form
- Interactions & Contraceptive Measures
- Katz Stirrat Hand Diagram
- Subject Drug Diaries
- Adverse Event/Serious Adverse Event Data
- Protocol Deviations
- Patient Questionnaires and Assessments
- Hand Examination Data

The following source data will not be directly collected in the Case Report Form (CRF) but will be captured in the electronic medical record (EMR).

- Laboratory results of safety labs
- Pregnancy Test results and Screening and Safety Lab results
- Concomitant Medications, Vital Signs, and Medical History
- Investigational Product administration
- Investigational Product tracking

The following source data will be received from the testing laboratory and stored in the electronic subject files

- Peripheral Blood and Urine results

## **4 Subject Selection, Enrollment, and Withdrawal**

### **4.1 Inclusion Criteria**

Subjects must meet all of the following inclusion criteria to be eligible for enrollment:

- Males and females between age 21 and 80 years of age.
- Symptoms of numbness or tingling for at least 4 weeks in at least two digits on one hand that include thumb, index, long, or radial border of ring finger.
- Classic or probable carpal tunnel syndrome on Katz-Stirrat hand diagram.
- A clinical diagnosis of carpal tunnel syndrome. Patients with bilateral CTS will have the more severe hand enrolled.
- Able to complete English-language questionnaires and clinical evaluations.
- Willingness to avoid pregnancy.
  - Female participants of childbearing potential must have a negative pregnancy test at screening (serum) and before the first dose on Day 1 (urine), before the third dose on Day 29 (urine), and 60 days after the final dose on day 60 (urine).
  - Sexually active female participants of childbearing potential must agree to take appropriate precautions to avoid pregnancy from screening until 30 days after the last dose of study drug (day 60). Permitted methods in preventing pregnancy (see Appendix A) will be communicated to the participants and their compliance confirmed.
  - All female participants of childbearing potential will refrain from donating oocytes from screening-day 60 of the study.
  - Women without child bearing potential (ie., surgically sterile with hysterectomy and/or bilateral oophorectomy and/or bilateral salpingectomy OR  $\geq 12$  months of amenorrhea and at least 50 years of age) are eligible to participate without the above precautions.
- Willing and able to comply with study procedures and requirements and attend all study visits as defined in this protocol.

## 4.2 Exclusion Criteria

Subjects with any of the following exclusion criteria will not be eligible for enrollment:

### 4.2.1 General Exclusion Criteria:

- Unable or unwilling to give informed consent.
- Pregnant or breast feeding
- Previous carpal tunnel release on the study hand
- History of steroid injection into carpal tunnel or surgery on the affected wrist within the past 6 months.

- Prisoners, institutionalized individuals, or others who may be considered vulnerable populations, such as individuals with dementia.

#### **4.2.2 Laboratory Exclusion Criteria:**

The following laboratory tests as indicated or as *per* clinical judgement:

- Bilirubin > 2.0; serum aspartate transaminase (AST) > 4 X upper limit of normal, or alanine aminotransferase (ALT) > 4 X upper limit of normal as a marker of liver disease
- Hemoglobin < 7g/dL; white blood cell count  $\leq$  2,000/mm^3 ( $\leq$  2.0 x 10^9/L) or  $\geq$  20,000/mm^3 ( $\geq$  20 x 10^9/L); platelet count  $\leq$  40,000/ $\mu$ L ( $\leq$  40 x 10^9/L); absolute neutrophil count  $\leq$  1 x 10^9/L; lymphocyte count  $<$  0.3 x 10^9/L at screening as a marker of poor nutrition
- Plasma and/or serum fasting glucose > 300 or HbA1c > 9 as a marker of poor diabetic control
- Creatinine > 2.5, cystatin c > 3 or eGFR < 25 ml/min/1.73 m^2 as a marker of advanced kidney disease,
- CRP > 10 or ESR > 25 as a marker of systemic inflammation
- Unstable (as per clinical judgement) major cardiovascular, renal, endocrine, immunological, or hepatic disorder

#### **4.2.3 Clinical History Exclusion Criteria**

- History of diverticulitis or diverticulosis with GI bleeding, as *per* clinical judgement
- Any of the following clinical diagnosis or conditions: cervical radiculopathy, renal failure (see laboratory exclusion criteria), liver disease (see laboratory exclusion criteria), peripheral nerve disease, uncontrolled diabetes (see laboratory exclusion criteria), or other metabolic disorder; as *per* clinical judgement
- Human immunodeficiency virus infection
- Known active hepatitis B or C infection
- Invasive fungal infection
- Uncontrolled (as per clinical judgement) pleural/pericardial effusions or ascites
- New/active invasive cancer except non-melanoma skin cancers

#### **4.2.4 Medication Exclusion Criteria**

- Known hypersensitivity or allergy to Fisetin or other flavonoids
- Currently participating in another study using Fisetin or currently taking any flavonoid as a nutritional supplement. Note that consuming foods rich in flavonoids is NOT an exclusion, both because flavonoids are present in almost all fruits and vegetables, making such an exclusion impossible as a practical matter, and, from a scientific perspective, the amount of flavonoids in general, and Fisetin in particular, present in foods is far lower than the dose that will be administered in the trial.

- Patients currently taking medications listed in the Investigator Brochure are excluded unless medication can be safely held following the guidelines in the Investigator Brochure .
- If the patient is required to initiate any medication listed in the Investigator Brochure during the study, the PI will reassess their continued participation in the study.

**4.2.5 Behavioral Modifications** - Participants will be educated about the risk of excessive caffeine usage and nicotine usage. Namely,

- CAFFEINE: limit daily intake to no more than the equivalent of 4 cups of coffee per day or 400 milligrams of caffeine per day.
- TOBACCO/NICOTINE: limit daily intake to no more than a pack of day (20 cigarettes) or 20 mg of nicotine per day.

Alternatively, if a subject routinely uses more than these amounts they can be considered for enrollment if a behavior modification program is in place that reduces the daily usage by half.

### 4.3 Subject Recruitment, Enrollment, and Screening

We will recruit patients from our Hand Clinic and other clinical areas at Mayo Clinic. We will also recruit via Mayo Clinic's social media outreach, facilitated by Research Recruitment Services of the Office of Clinical Trials. All subjects will be screened before they receive the first dose of study drug (i.e., screening on Days -14 to Day -1 and study drug administration on Days 0,1,29, 30). Adult patients who meet the inclusion and exclusion criteria will be offered enrollment into the study. We will make every effort to recruit minorities. The minority population in our local community is roughly 10%. Monthly meetings of the PI and study coordinator will assure steady progress towards accomplishing the recruitment goals.

### 4.4 Early Withdrawal of Subjects

#### 4.4.1 When and How to Withdraw Subjects

All subjects will be assessed during the 2 days of medication administration, subsequent days of medication administration, and all study visits. If a severe adverse event (SAE) occurs at any time during administration of the 2-day drug regimen, a formal review will occur, and subsequent patients will be enrolled one at a time using the same regimen. If three or more events accrue, the pilot study will be held and either a potential dosing regimen revisited, or discontinuation of the study protocol will occur. Other interventions will be at the direction of the Food and Drug Administration and Mayo Institutional Review Board.

Patients may also wish to withdraw if they perceive that their symptoms of carpal tunnel syndrome are not improving, and they wish additional treatment such as surgery or a steroid injection. If they are tolerating the Fisetin otherwise, we will request that they continue the Fisetin in addition to the other treatments, and such patients will continue to be followed, but will be excluded from the final analysis. We aim to continue enrollment until 40 patients complete the 60-day trial time point without intervening treatment for their CTS.

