### **Premature withdrawal from study:**

Subjects may voluntarily withdraw from the study for any reason at any time. Subjects are considered withdrawn if they state an intention to withdraw further participation in all components of the study, die, or are lost to follow-up for any other reason. The investigator may withdraw a subject from the study (without regard to the subject's consent) if they believe that continued participation in the study would be contrary to the best interests of the patient.

Subjects are considered as lost to follow-up if all reasonable attempts by the investigator to communicate with the individual fail. The investigator will take preventive measures to avoid a subject being lost to follow-up (*e.g.*, document different ways of contact such as telephone number, home address, e-mail address, person to be contacted in case the subject cannot be reached). If the subject cannot be reached, the investigator will make a reasonable effort to contact the subject, document all attempts and enter the loss of follow-up information into the Case Report Form (CRF). The following methods will be used: at least two telephone calls will be placed to the last available telephone number (each call on different days) and one registered letter will be sent by post to the last available home address. If the subject is still unreachable after all contact attempts listed above, he/she will be lost to follow-up.

If premature withdrawal occurs for any reason, the reason for premature withdrawal from the study, along with who made the decision (subject, investigator) will be recorded in the CRF.

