### **Subject replacement:**

Subjects withdrawn from the study will be replaced by newly recruited subjects meeting inclusion criteria matching similar baseline characteristics (age, gender, race, , and/or blood or urine assay senescence marker positivity).

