#### **4.4.2 Data Collection and Follow-up for Withdrawn Subjects**

For safety monitoring, telephone contact of withdrawn subjects receiving Fisetin will be attempted. Research data will not be collected on subjects after they are withdrawn from the study, any additional evaluation will be for subject safety only.

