### 7.3 Subject Population(s) for Analysis

As a pilot study, all subjects who complete the 60-day study visit ( $60 \pm 5$  days) will be the main population of interest, though summaries will be made of those who do not reach that point.

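### Section 4.4.1 drops patients who seek injection or surgery for non-improvement, which tilts the single-arm mean change toward benefit; 7.3 omits this rule and section 7 plans no all-dosed analysis

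*Combined protocol and SAP*

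**What the plan says.** In this point, rescue means a steroid injection or surgery for CTS before Day 60.

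- **4.4.1, trigger.** "Patients may also wish to withdraw if they perceive that their symptoms of carpal tunnel syndrome are not improving" and want an injection or surgery. Those who tolerate fisetin are asked to continue it.
- **4.4.1, analysis rule.** "such patients will continue to be followed, but will be excluded from the final analysis".
- **4.4.1, target.** "We aim to continue enrollment until 40 patients complete the 60-day trial time point without intervening treatment for their CTS".
- **7.3.** The population is "all subjects who complete the 60-day study visit" (60 ± 5 days); these "will be the main population of interest, though summaries will be made of those who do not reach that point". Rescue is not mentioned.
- **7.2.** The primary analysis is a confidence interval for the BCTQ change with a paired t-test, and the emphasis is on the interval. A mixed model using every BCTQ measurement is secondary. The missing-data paragraph offers only demographic and baseline BCTQ summaries of dropouts against Day 60 completers.
- **4.4.1, Premature withdrawal.** "Subjects are considered withdrawn if they state an intention to withdraw further participation in all components of the study", die or are lost to follow-up. Under Subject replacement, "Subjects withdrawn from the study will be replaced by newly recruited subjects meeting inclusion criteria". Under 4.4.2, "Research data will not be collected on subjects after they are withdrawn from the study".
- **5.5.** Injection and surgery are the two CTS treatments not allowed in the first 60 days.

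**The concern.** The primary endpoint is symptom improvement at Day 60, and the route out of the analysis is perceived lack of improvement. Patients doing badly are removed and further enrolment fills their places until 40 rescue-free completers exist. The Study Summary asks whether fisetin has any effect, and the only contrast is before versus after, so no comparator with the same selection offsets this. Section 1.1 makes the result the basis for a Phase 3 trial.

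Section 7 does not repair this. A rescued patient who attends Day 60 is neither a dropout nor someone who failed to reach Day 60, so neither planned summary describes that patient separately. The text on the mixed model does not say whether rescued patients, or their scores after rescue, enter it. An analyst working from section 7 alone would keep the post-rescue score and count it as a fisetin effect, although section 1.1 describes the alternative treatments as effective.

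**Working it through.** **Inputs from the plan (7.1, 4.4.1).** SD of change 0.7, significance level 0.05, paired t-test, 40 rescue-free completers. Sidedness is not stated; two-sided is used because it reproduces the plan's figures.

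**Assumptions (not in the documents).** True mean change 0; share rescued f = 5%, 10% or 20%; correlation rho = 0.3 to 0.5 between the tendency to seek rescue and lack of improvement in the Day 60 change that would have occurred without rescue. Improvement is counted as positive.

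**Step 1: the plan's own figure.** The noncentral t with 39 df gives a minimum detectable change of 0.318 (80% power) and 0.368 (90%). The normal approximation gives (1.960 + 0.842) × 0.7/√40 = 0.310 and (1.960 + 1.282) × 0.7/√40 = 0.359. Both round to the stated 0.3/0.4. The sample-size statement is sound; the problem is who is analysed.

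**Step 2: precision.** 95% CI half-width = t(0.975; 39) × 0.7/√40 = 2.023 × 0.1107 = 0.224.

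**Step 3: bias under the 4.4.1 rule.** Shift = rho × 0.7 × φ(z_f)/(1 − f), where z_f is the normal quantile at f.

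- f = 5%: 0.7 × 0.1031/0.95 = 0.0760
- f = 10%: 0.7 × 0.1755/0.90 = 0.1365
- f = 20%: 0.7 × 0.2800/0.80 = 0.2450

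These are multiplied by rho. False positives (significant improvement when there is none, nominal 2.5%) come from 40,000 simulated trials per scenario, each enrolling until 40 are not rescued.

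| Rescued | Shift, rho 0.3 / 0.5 | Share of half-width | False positives, rho 0.3 / 0.5 | Dosed to reach 40: 40/(1 − f) |
|---|---|---|---|---|
| 5% | 0.023 / 0.038 | 10% / 17% | 3.8% / 5.1% | 43 |
| 10% | 0.041 / 0.068 | 18% / 30% | 5.4% / 8.7% | 45 |
| 20% | 0.073 / 0.122 | 33% / 54% | 9.7% / 20.5% | 50 |

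The largest simulated upper confidence limit was 0.86, so none reached 1.0.

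**Step 4: 7.3 applied without 4.4.1.** If rescue adds b points (assumed 0.5 to 1.0), the shift is f × b: 0.025-0.05, 0.05-0.10 and 0.10-0.20 at 5%, 10% and 20% rescue. This also favours fisetin.

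**Step 5: what an all-dosed analysis would do.** Assigning rescued patients a worsening w leaves a residual bias of (1 − f) × shift − f × w. Over f = 5-20% and rho 0.3-0.5:

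- w = 0 leaves +0.02 to +0.10
- w = 0.5 leaves −0.04 to +0.01
- w = 1.0 leaves −0.14 to −0.01

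The mixed model on baseline and pre-rescue scores was also simulated, optimistically assuming a pre-rescue change observed on everyone, correlated 0.5-0.8 with the Day 60 change. If rescue follows the pre-rescue score, the bias is 0.00. If it follows the later outcome, 0.03-0.09 remains at 20% rescue and rho 0.3-0.5. A patient rescued before Day 29 has only a baseline score. The model therefore reduces the bias but does not remove it, so a tipping-point analysis is needed beside it.

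**The case against.** **The two sections can be read together.** 4.4.1 is the specific rule and 7.3 the general one; jointly they give rescue-free completers. A reader might infer two contradictory primary populations, one of which counts post-rescue scores. The documents do not force that: it arises only if section 7 is applied without 4.4.1. What stands against the plan is that 7.3, where an analyst looks for the population, omits the exclusion.

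**Rescued patients are not clearly withdrawn.** A reader might infer that they are replaced and their data collection stopped. But withdrawal is defined as leaving all components of the study, and 4.4.1 keeps these patients in follow-up, so the replacement paragraph and 4.4.2 do not clearly reach them. One clarifying sentence is enough.

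**5.5 and 4.4.1 need not conflict.** One states a restriction and the other what follows in the analysis if it is not kept. Likewise, 4.4.1 says which 40 is the target; only the Study Summary's figure is loose.

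**The size is assumed, and modest at low rescue.** This is right. At 5-10% rescue the shift is under a third of the CI half-width. The false-positive rates concern a test against zero while 7.2 emphasises the interval, but the same shift moves the interval. Perfect correlation would give a shift of 0.245 at 20% rescue; nothing in the documents supports so extreme a case, and the conclusion does not use it. Natural course can also move a before-after mean, and no choice of population cures that.

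**All-dosed as primary is a choice of estimand.** Reasonable statisticians could keep rescue-free completers as primary in a pilot. The point therefore asks for one stated population and an all-dosed analysis beside it, not for a particular primary population.

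**Conclusion.** The concern holds and should be fixed. In this uncontrolled trial the 4.4.1 exclusion depends partly on the outcome and biases the mean change and its interval toward benefit. Section 7.3 does not carry the rule, and section 7 offers only descriptive summaries of patients who drop out or miss Day 60. The direction follows from the plan's own trigger for rescue. The size does not: the shift of 0.02 to 0.12 points, against a half-width of 0.22, and the false-positive rates of about 4% to 20%, against 2.5%, rest on the assumed rescue rates, correlations and zero true change.

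A reader might infer that the exclusion could manufacture the hypothesised 1-point improvement. It could not under these assumptions. What it can affect is the smaller question of whether there is any improvement at all.

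**What to change.** 1. Make 4.4.1 and 7.3 state the same primary population and the same rule for patients with an injection or surgery before Day 60, so that post-rescue scores are not counted as fisetin effect.
2. Replace the blanket exclusion with a pre-specified analysis of all patients who receive at least one dose, reported beside the paired t-test and CI in rescue-free completers. Use the mixed model already planned in 7.2, restricted to baseline and pre-rescue BCTQ. Add a tipping-point analysis that assigns rescued patients no change and then increasing worsening, and report the worsening at which the CI first includes 0. Do not present any fixed range of worsening as a bound on the bias.
3. Report the numbers dosed, rescued and withdrawn, with reasons. State in 4.4.1 that followed, rescued patients are not withdrawn for the purposes of 4.4.2, so their data collection continues.
4. Align the Study Summary's 40 enrolled with the 40 rescue-free completers in 4.4.1. At 5%, 10% and 20% rescue, that target needs about 43, 45 and 50 dosed patients, before any other dropout.

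The cost is wording in the Study Summary, 4.4.1, 7.2 and 7.3, slightly more analysis work, and a somewhat less favourable estimate in the all-dosed analysis. The changes do not separate drug effect from natural course, which a single arm cannot do.
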